3.2.7 Overall survival landmark summary

OS is defined as the time from the date of randomisation until death due to any cause (i.e., date of death or censoring – date of randomisation + 1). Any patient not known to have died at the time of the summary will be censored based on the last recorded date on which the patient was known to be alive (SUR_DAT, recorded within the SURVIVE module of the eCRF).

Note: Survival calls which were originally planned for the 2 weeks following the date of data cut-off (DCO), will no longer be made following approval of CSP version 2.0.

The proportion of patients alive at 12 months (i.e., OS12) will be defined as the KM estimate of OS at 12 months

3.3 Safety variables

Following approval of CSP version 2.0 safety assessments will not be collected for Group A patients, except for SAEs.

3.3.1 Adverse Events

All AEs will be coded using the latest version of the Medical Dictionary for Regulatory Activities (MedDRA) and graded according to the National Cancer Institute CTCAE (version 4.0.3 or later).

Preferred terms used to identify adverse events of special interest (AESI) will be listed before database lock and documented in the Study Master File. Groupings of certain MedDRA preferred terms will be based on preferred terms provided by the medical team and a listing of the preferred terms in each grouping will be produced.

The grouped preferred terms for AESI for AZD9291 are shown below. A separate list will be produced for MEDI 4736. The individual preferred terms will be available in the programming specification documentation:

- Ocular surface effects
- Dry eye/conjunctivitis
- Interstitial lung disease and acute interstitial pneumonitis
- Nail and nail bed conditions
- Skin disorders including dermatitis
- Upper GI tract inflammatory events
- Cardiotoxicity
- Diarrhoea

- Colitis/Enterocolitis (Gastrointestinal Disorder)
- Hepatitis/ Hepatic Toxicity (Hepatic Function Abnormality)
- Infusion-related Reactions
- Anaphylaxis and Serious Allergic Reactions (Hypersensitivity)
- Neuromuscular Toxicity/Neuropathy
- Endocrinopathy

Any AE occurring before study treatment will be included in the data listings but will not be included in the summary tables of AEs.

Any AE occurring within 30 days of discontinuation of AZD9291 and within 90 days for MEDI4736 will be included in the AE summaries. Any events in this period that occur after a subject has received further therapy for cancer (following discontinuation of AZD9291) will be flagged in the data listings. If AZD9291 is discontinued less than 60 days after MEDI4736, subjects should be followed up to 90 days from the date of MEDI4736 discontinuation.

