1. STUDY DETAILS

1.1 Study objectives

Primary objective

Objective:	Outcome Measure:
To investigate the safety and tolerability profile of AZD9291 in combination with MEDI4736.	Adverse events (graded by Common Terminology Criteria for Adverse Events (CTCAE v4)) Clinical chemistry, haematology and urinalysis Vital signs (pulse and blood pressure), Physical Examination, Weight Digital Electrocardiogram (ECG) Echocardiogram/Multi Gated Acquisition Scan (MUGA) (for Left Ventricular Ejection Fraction) WHO Performance Status

Exploratory objectives

Objective:	Outcome Measure:
To assess the safety and tolerability of AZD9291 as a single agent	Adverse events (graded by CTCAEv4) Clinical chemistry, haematology and urinalysis Vital signs (pulse and blood pressure), Physical examination, Weight Centrally reviewed digital Electrocardiogram (ECG) Echocardiogram/Multi gated Acquisition Scan (MUGA) (for left ventricular Ejection fraction) WHO performance status Serious Adverse events (graded by CTCAEv4)

Objective:	Outcome Measure:
To obtain a preliminary assessment of the efficacy of AZD9291 in combination with MEDI4736 and AZD9291 monotherapy	Objective Response Rate (ORR) Progression Free Survival (PFS) landmark at 6 and 12 months Overall Survival (OS) landmark at 12 months Duration of Response (DoR) Disease Control Rate (DCR) Tumour shrinkage using Investigator assessments according to RECIST 1.1
To assess the PK of AZD9291 as a single agent and in combination with MEDI4736.	Plasma concentrations of AZD9291 and metabolites AZ5104 and AZ7550.
To characterise the PK and immunogenicity of MEDI4736 after single dosing and at steady state after multiple dosing when given intravenously to patients with EGFRm non small-cell lung cancer (NSCLC) in combination with AZD9291	Plasma concentrations of MEDI-4736 to characterise PK Blood samples for anti-drug antibodies (ADA) to characterise immunogenicity.
The following exploratory objectives may be reported separately from the main Clinical Study Report (CSR) and will not be covered in this Statistical Analysis Plan.	
To characterise the pharmacodynamics of MEDI4736 after single dosing and at steady state after multiple dosing when given intravenously to patients with EGFRm non small-cell lung cancer (NSCLC) in combination with AZD9291	Blood samples for soluble PD-L1 to characterise pharmacodynamics .

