1.3 Number of subjects

The original plan was to recruit approximately 350 subjects, stratified by current line of treatment (2nd/3rd line plus) and ethnicity (Asian/non-Asian), randomized in a 1:1 ratio to the treatments as specified below:

- AZD9291 80mg QD
- AZD9291 80mg QD and MEDI4736 10mg/kg q2w

The study was terminated early with only 29 patients randomized. This number is not considered sufficient for statistical comparison of the treatment groups, and all data reporting will be using summaries and listings.

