4.2.8.1 Adverse events

All AEs, both in terms of MedDRA PT and CTCAE grade, will be listed and summarized descriptively by count (n) and percentage (%) for each treatment group. MedDRA will be used for coding. Any AE occurring before study treatment (i.e., before Study Day 1) will be included in the AE listings, but will not be included in the summary tables (unless otherwise stated). These will be referred to as 'pre-treatment'. The summary tables will include all AEs that occurred after the start of treatment up until the end of the follow-up period.

All reported AEs will be listed along with the date of onset, date of resolution (if AE is resolved), investigator's assessment of severity and relationship to study drug. Frequencies and percentages of subjects reporting each preferred term will be presented (i.e., multiple events per subject will not be accounted for apart from on the episode level summaries).

Summary information (the number and percent of subjects by treatment) will be tabulated for:

- All AEs
- All AEs causally related to study treatment

- AEs with CTCAE grade 3 or higher
- AEs with CTCAE grade 3 or higher, causally related to study treatment
- Fatal AEs
- All SAEs
- AEs leading to discontinuation
- OAEs

An overall summary of the number and percentage of subjects in each category will be presented, as will an overall summary of the number of episodes in each category. In addition, a truncated AE table of the most common AEs, showing all events that occur in at least 5% of subjects overall will be summarized by preferred term, by decreasing frequency. This cut-off may be modified after review of the data.

AEs will be assigned CTCAE grades and summaries of the number and percentage of subjects will be provided by maximum reported CTCAE grade, SOC, PT and actual treatment group.

In addition, AEs with an outcome of death, SAEs, and OAEs will be listed.

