4.2.8.2 AEs of special interest

Summary tables of AESIs will be produced. The number (%) of patients experiencing any of the specified terms will be presented overall, by maximum CTCAE grade, and by outcome.

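### The AE summary tables exclude pre-treatment events with no stated exception for worsening after first dose, so an event that becomes severe or serious on treatment can be left out if the worsening stays on its original record

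*SAP*

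**What the plan says.** Section 3.3.1 sets the rule: "Any AE occurring before study treatment will be included in the data listings but will not be included in the summary tables of AEs". Section 4.2.8.1 repeats it with a proviso, saying that such events "will be included in the AE listings, but will not be included in the summary tables (unless otherwise stated", and labels them pre-treatment. It then gives the positive side of the rule: "The summary tables will include all AEs that occurred after the start of treatment up until the end of the follow-up period".

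The severity tables are described as "AEs will be assigned CTCAE grades and summaries of the number and percentage of subjects will be provided by maximum reported CTCAE grade", broken down further by SOC, PT and actual treatment group. For events of special interest, section 4.2.8.2 says: "The number (%) of patients experiencing any of the specified terms will be presented overall, by maximum CTCAE grade, and by outcome". Neither output has an inclusion rule of its own.

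The primary objective in section 1.1 is "To investigate the safety and tolerability profile of AZD9291 in combination with MEDI4736", and CTCAE-graded adverse events head its outcome measures. On size, section 1.3 says: "The study was terminated early with only 29 patients randomized".

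**The concern.** A treatment-emergent definition normally has two limbs: events that begin on treatment, and events that were present earlier and worsen on treatment. The SAP writes only the first. A grade 1 rash, diarrhoea or respiratory event noted at screening that reaches grade 3 on study drug, or becomes serious, could be classed as pre-treatment and appear only in a listing.

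AE tables are main outputs here because safety is the primary objective. The patients had progressed on an earlier EGFR-TKI and had a mandatory biopsy, so low-grade events before first dose are plausible, though the SAP gives no data on them. Skin disorders, diarrhoea and interstitial lung disease are among the special-interest groups, and enrolment stopped because of lung events with this combination in another study. Any omission of this kind lowers reported rates and cannot raise them.

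**Working it through.** The SAP states no figure on this point, so there is none to reproduce. The check is a reading of the AE sections, followed by simple proportions for scale.

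**Step 1: is there a worsening rule anywhere?**
- 3.3.1: events before study treatment go to the listings, not the tables. Worsening is not mentioned.
- 4.2.8.1: the same exclusion, with a proviso that an exception may be stated elsewhere, and inclusion of events that occurred after treatment started. Worsening is not mentioned.
- 3.3.2, 4.2.8.2 and 4.2.8.3 (other significant AEs, special interest, deaths): no exception for worsening.
- Elsewhere in the SAP, worsening is used only for non-target lesions.

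The proviso is therefore never used.

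**Step 2: what happens to an event that starts at grade 1 before first dose and reaches grade 3 afterwards?**
- *New record opened at worsening:* the new record starts after first dose and is counted. No effect.
- *Worsening kept on the original record:* the start date is before first dose. Read by start date, the event is pre-treatment and is left out of every table that inherits the rule: all AEs, grade 3 or higher, SAEs, discontinuations, maximum grade and special interest.

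The SAP does not state the convention, so the table counts depend on something outside its text.

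**Step 3: where is the boundary?**
- 4.2.8.1 glosses pre-treatment as before Study Day 1.
- 4.1.2 defines Study Day 1, for efficacy, as the date of randomisation. For safety it defines Dose Day 1 as the date of first dose.
- An AE between randomisation and first dose is therefore not before Study Day 1, yet it did not occur after treatment started. One sentence of 4.2.8.1 does not exclude it; another does not include it.

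**Step 4: scale.** Inputs: 29 randomised (section 1.3); 1:1 allocation (section 1.3); a 5% overall cut-off for the common-AE table (section 4.2.8.1). Assumptions: all 29 are in the Safety Analysis Set, and the arms are 14 and 15, since arm sizes are not given.
- One omitted patient overall: 1/29 = 3.4%.
- One omitted patient in an arm: 1/15 = 6.7% to 1/14 = 7.1%.
- Patients needed to reach the cut-off: 0.05 × 29 = 1.45, so 2 patients (2/29 = 6.9%). One patient (3.4%) falls short, so omitting one of two patients would remove a preferred term from that table.

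**The case against.** The strongest reply is that the text speaks of events occurring, not of onset. An episode that reaches grade 3 after first dose can be read as having occurred after treatment started. What counts as an AE, and whether a grade change opens a new record, are commonly left to the protocol and the eCRF instructions, which are not shown. This stands in part: a reader might infer that the SAP certainly drops these events and biases severe-event rates downward, and the document does not support that. The effect is conditional and may be nil.

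A reader might also take the reference to a maximum reported grade as proof that one record carries several grades. It is not. The tables count subjects, and a subject can have several events under one term, which is reason enough for a maximum.

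Other outputs limit the harm. All AEs are listed with onset, resolution, severity and relationship. SAEs and fatal events are also listed, deaths are tabulated without an AE-onset criterion, and laboratory values are graded separately. With 29 patients and no hypothesis tests, a reader can go through the listings.

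On the boundary, Study Day 1 may be loose wording for first dose; even so, it conflicts with the SAP's own definitions.

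What remains is that the SAP itself fixes, in two places, which AEs enter the tables, and leaves the worsening case unresolved. Listings do not correct a count in a primary safety table.

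**Conclusion.** The point holds conditionally. As written, the rule excludes pre-treatment AEs and makes no exception for worsening after first dose. Where worsening is recorded on the original AE with its pre-treatment start date, an event that becomes more severe or serious on treatment can be left out of the main safety tables, while remaining in the listings. Where a new record is opened, there is no effect.

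The number of affected events is unknown and may be zero. Each omitted patient would cost 3.4 percentage points overall, or about 7 in one arm, under the assumptions on the safety set and arm sizes given above. The mismatch between Study Day 1 and Dose Day 1 does not depend on the eCRF convention and should be corrected in any case.

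**What to change.** In sections 3.3.1 and 4.2.8.1, replace the current rule with one along these lines: AE summary tables include (a) AEs with onset on or after first dose (Dose Day 1), and (b) AEs with earlier onset that increase in CTCAE grade or become serious on or after first dose, within the follow-up window. Count events under (b) at the maximum grade reached after first dose or, if grade changes are not dated, at the recorded maximum grade. Pre-treatment AEs that do not worsen stay in the listings only. Remove the reference to Study Day 1 from the AE rule.

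The cost is a wording change in two sections and a programming flag. The SAP does not show that dated grade changes are collected, which is why the fallback is needed; using it may attribute to treatment a grade already reached before first dose. Reported AE rates may be slightly higher. If the eCRF already opens a new record at worsening, the grade-worsening limb should leave the counts unchanged.

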1.2 Study design

This trial was initially designed as a phase III, multi-centre, open label, randomized study to assess the efficacy and safety of AZD9291 (80 mg, orally, once daily) in combination with MEDI4736 (10 mg/kg, IV infusion every 2 weeks [q2w]) versus AZD9291 monotherapy (80 mg, orally, once daily) in patients with a confirmed diagnosis of EGFR T790M mutation positive (T790M+) locally advanced or metastatic NSCLC (Stage IIIB-IV), who have progressed following prior therapy with an approved EGFR-TKI agent.

All patients must have documented radiological progression on EGFR-TKI treatment and on the last treatment administered prior to enrolling in the study.

A mandatory biopsy was needed for central testing of T790M mutation status following confirmed disease progression on previous treatment.

Three hundred fifty patients were planned to be randomized, however recruitment was stopped after enrolling 29 patients. Early termination of enrolment into the study was decided in the light of a higher than anticipated incidence of interstitial lung disease-like events in patients receiving the combination of AZD9291 with MEDI4736 in a separate multi-arm Phase 1b open label study D5160C00006 (TATTON).

Two summaries of the study data are planned:

Primary Summary

A primary summary will be performed with a data cut-off date representative of when the last country with active patients receives ethics and regulatory approval for protocol version 2.0. This summary will be used for the CSR and will report data according to the randomised or actual treatment groups as specified in [Section 2](#).

Final Summary

Patients had been initially randomized to receive either AZD9291 in combination with MEDI4736 or AZD9291 monotherapy. Depending on the treatment being received, the patients will be categorized as follows for the purpose of delineating the required study plan and assessments:

GROUP A - Patients on AZD9291 monotherapy

Group A includes patients continuing to receive AZD9291 monotherapy following data cut-off (DCO) for the primary analysis, who were either randomised to receive AZD9291 monotherapy or were randomised to receive AZD9291 in combination with MEDI4736 but who have discontinued MEDI4736 and been followed up for 90 days post discontinuation of MEDI4736

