2.1.2 Safety Analysis Set

The Safety Analysis Set will consist of all subjects who received at least one dose of randomized treatment. Safety data will be summarized using the Safety Analysis Set, according to the treatment that patients received in their first cycle. Patients who received at least one dose of MEDI4736 in the first treatment cycle (15 +/-3 days) will be regarded as being in the combination treatment. Additional summaries might be provided for the patients who were randomised and received the combination but later discontinued MEDI4736 as appropriate.

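### For combination patients who stop AZD9291 less than 60 days after MEDI4736, the AE tables count up to 60 more off-treatment days than for monotherapy patients, and no common-window AE overview is planned

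*SAP*

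**What the plan says.** The AE window is set in SAP section 3.3.1: "Any AE occurring within 30 days of discontinuation of AZD9291 and within 90 days for MEDI4736 will be included in the AE summaries". The same paragraph adds that AEs falling inside these windows "that occur after a subject has received further therapy for cancer (following discontinuation of AZD9291) will be flagged in the data listings". It states no exclusion from the tables. It then says when the longer limit governs: "If AZD9291 is discontinued less than 60 days after MEDI4736, subjects should be followed up to 90 days from the date of MEDI4736 discontinuation".

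Section 4.2.8.1 gives the scope, "The summary tables will include all AEs that occurred after the start of treatment up until the end of the follow-up period", and the metric: events are "summarized descriptively by count (n) and percentage (%) for each treatment group". It plans no exposure-adjusted or follow-up-adjusted rate, no AE overview on a window common to both arms, and no table cut at the next cancer therapy.

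Section 2.1.2 fixes the columns by first-cycle treatment: "Patients who received at least one dose of MEDI4736 in the first treatment cycle (15 +/-3 days) will be regarded as being in the combination" group. A patient who later drops MEDI4736 stays in that column. Section 1.2 (Group A) foresees such patients, namely those randomised to the combination "who have discontinued MEDI4736 and been followed up for 90 days post discontinuation of MEDI4736" who go on taking AZD9291.

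On comparison of the arms, section 1.3 says of the 29 randomised patients: "This number is not considered sufficient for statistical comparison of the treatment groups, and all data reporting will be using summaries and listings". Section 4 rules out hypothesis testing.

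**The concern.** The safety and tolerability of the combination is the only primary objective (section 1.1), and crude percentages by treatment group are how most of the AE data will be read. A longer ascertainment window can add patients to a crude percentage but can never remove one. If one column counts 90 days after the last dose and the other 30, two equally toxic regimens can show different percentages.

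Events that begin after the next cancer therapy make this harder to read. They are kept in both columns, so keeping them favours neither arm in itself. A longer window, however, leaves more room for them.

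Section 1.2 says enrolment stopped because of a toxicity signal with the same combination in another study, so readers are likely to set the two columns against each other even though no test is planned.

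**Working it through.** **Inputs from the SAP.** 30 days after AZD9291 and 90 days after MEDI4736 (section 3.3.1); the 60-day threshold (section 3.3.1); 1 month = 30.4375 days (section 4.1); 29 patients randomised (section 1.3). The end of follow-up in section 4.2.8.1 is read as the end of the section 3.3.1 windows.

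**Step 1: reproduce the plan's own threshold.** Let g be the days from stopping MEDI4736 to stopping AZD9291. The window of a combination patient ends at the later of AZD9291 stop + 30 and MEDI4736 stop + 90. The 90-day limit governs when g + 30 < 90, that is g < 60. This agrees with the SAP.

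**Step 2: extra off-treatment days.** For g of 0 or more, the days counted after the last AZD9291 dose are max(30, 90 − g). A monotherapy patient has 30. The excess is max(0, 60 − g).

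| Gap g (days) | Days counted after AZD9291 | Excess over monotherapy |
|---|---|---|
| 0 | 90 | 60 |
| 15 | 75 | 45 |
| 30 | 60 | 30 |
| 45 | 45 | 15 |
| 59 | 31 | 1 |
| 60 or more | 30 | 0 |

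If MEDI4736 is the last drug stopped, off-treatment time runs from its last dose and the excess is 90 − 30 = 60 days. For a patient still on treatment at data cut-off there is no off-treatment window and no excess.

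**Step 3: what this can do to a crude percentage.** The SAP gives no AE rates, safety-set arm sizes, stopping gaps or timing of next therapy, so this step is an illustration only. Assumptions: the same monthly hazard h in both arms, the same time on treatment T (months), both drugs stopped on the same day, everyone off treatment and followed for the full window. The percentage with an event is 1 − exp(−h·t), with t = T + 30/30.4375 for monotherapy and T + 90/30.4375 for the combination.

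Worked case, T = 6 and h = 0.03: monotherapy 1 − exp(−0.03 × 6.986) = 18.9%; combination 1 − exp(−0.03 × 8.957) = 23.6%; difference 4.7 points.

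| T (months) | h = 0.01 | h = 0.03 | h = 0.10 | h = 0.30 |
|---|---|---|---|---|
| 2 | 2.9 vs 4.8% | 8.6 vs 13.8% | 25.8 vs 39.1% | 59.2 vs 77.4% |
| 6 | 6.7 vs 8.6% | 18.9 vs 23.6% | 50.3 vs 59.2% | 87.7 vs 93.2% |
| 12 | 12.2 vs 13.9% | 32.3 vs 36.2% | 72.7 vs 77.6% | 98.0 vs 98.9% |

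The difference runs from 0.9 to 18.2 points, or 0.14 to 2.73 patients in an assumed arm of 15. It is small for events that almost everyone has. A 30-day gap gives about half: 2.4 instead of 4.7 points in the worked case. A gap of 60 days or more gives zero.

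**Step 4: contribution of next-line therapy.** Suppose the hazard doubles from day 30 after stopping. At T = 6 the differences for h = 0.01, 0.03 and 0.10 become 3.6, 9.0 and 16.2 points.

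A second illustration counts only first grade 3 or higher events on the next therapy. It assumes that this therapy starts on day 21, that a share s of patients start it, that 60% have had no earlier such event, and a monthly event probability p. The excess is s × 0.6 × [(1 − p)^(9/30.4375) − (1 − p)^(69/30.4375)]. With s = 0.5 and p = 0.10 this is 0.5 × 0.6 × (0.969 − 0.788), about 5.5 points. From s = 0.3, p = 0.05 to s = 0.7, p = 0.20 it runs from 1.7 to 14.0 points. Both drugs are again assumed to stop together.

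**Step 5: after the fix.** With one cut at 30 days after the last dose of any study drug, the excess is 0 days at every gap, and the step 3 difference is 0 points.

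**The case against.** The strongest reply is that no contrast between the arms is planned. The primary objective describes the combination, and monotherapy safety is a separate exploratory objective. The study closed at 29 patients and nothing is tested. For describing the combination on its own, a window specific to MEDI4736 is defensible and errs towards inclusion. That stands, and it is why the full-window tables should remain. It does not remove the risk in reading two crude percentages side by side when no model or test accompanies them.

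The SAP also has partial safeguards. The death summary in section 4.2.8.3 separates fatal AEs more than 30 days after the last dose. Section 4.2.8.1 tabulates causally related AEs, although these depend on the investigator's attribution. Post-therapy events are flagged in the listings, and section 4.1.2 defines days since last dose for them. With 29 patients, a careful reader could rebuild a common window case by case. This lowers the stakes, but the all-AE, grade 3 or higher and SAE tables still have no such split.

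A reader might infer that combination AE rates rise by construction across the whole arm. The SAP does not support this: the excess shrinks with the gap and is nil at 60 days or more or when treatment is ongoing, and section 1.2 foresees patients who stay on AZD9291 after MEDI4736. A reader might also infer that the main tables should be truncated. That could lose delayed events from the tables of the primary objective, and the point does not require it.

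**Conclusion.** The point holds within limits. For combination patients who stop AZD9291 less than 60 days after MEDI4736, sections 3.3.1 and 4.2.8.1 count 60 minus the gap more off-treatment days than for monotherapy patients, to a maximum of 60. This follows from the SAP's own figures without assumption. Crude all-AE, grade 3 or higher and SAE percentages can therefore differ between columns without a true difference, and the longer window can take in more events on next-line therapy.

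The size cannot be derived from the SAP. The range of about 1 to 18 points rests on equal hazards, equal time on treatment, and every patient stopping both drugs together and being fully followed, which is the least favourable pattern. If only half the arm did so and the rest had no excess, the range would halve. In an arm of 15, one patient is 1/15 = 6.7 points, so most of these scenarios amount to between a fraction of a patient and two.

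Reporting is descriptive and fatal AEs already have a 30-day split, so this is a low-cost improvement to the presentation and no conclusion of a test is at risk.

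**What to change.** Leave the full-window main tables, the listings and patient follow-up as they are. Add to section 4.2.8.1 one supplementary AE overview for both arms covering all AEs, grade 3 or higher, SAEs and fatal AEs. Limit it to events from the first dose up to the earlier of (a) 30 days after the last dose of any study drug and (b) the start of subsequent anti-cancer therapy. Label it as the table for side-by-side reading.

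Footnote both sets of tables. The main tables should state the 30-day and 90-day windows and that events after further cancer therapy are included. The supplementary table should state that after approval of CSP version 2.0 only SAEs are collected for Group A (sections 1.2 and 3.3), which a common window does not correct. Nor does it adjust for different time on treatment.

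The cost is one extra table set and a few lines of SAP text. No new data are needed, because the start date of subsequent therapy is already used for response (sections 3.2.2 and 3.2.5) and for the listing flag. The downside is that the added table omits late events, all of which remain in the main tables.
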